13.12 Subject Withdrawal

Each subject is free to discontinue from the study at any time, for any reason. If a subject discontinues the study, the Investigator will record the reason for withdrawal on the CRF. Examples of reasons for premature withdrawal of a subject from the study include:

- Current illness that would, in the judgment of the Investigator, affect study assessment to a significant degree
- Subject noncompliance with follow-up assessments
- · Subject request to withdraw
- Subject lost to follow-up
- Termination of the site's study participation by Anika Therapeutics, Inc., the institution or IRB/EC
- Other (reason to be documented in the CRF)

Every effort shall be made to have withdrawn subjects return for the required safety evaluations as detailed in the protocol.

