2.0 Study Design

This is a prospective, expanded indications multi-center, open-label study to evaluate safety and performance of injection of Cingal for relief of pain in patients with a diagnosis of an osteoarthritic hip joint (CINGAL 20-01), shoulder joint (CINGAL 20-02), and ankle joint (CINGAL 20-03).

The subjects in each of these studies will be patients with a diagnosis of osteoarthritic (OA) joint who the investigator determines are appropriate candidates for treatment with an injection of CINGAL.

In each study, up to 25 subjects will be enrolled and treated at up to 10 investigational sites in the EU. Subject participation will last approximately 6 Months, with visits scheduled at Screening, Baseline, 1 month, 3 month and 6 months.

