4.0 Statistical Methods in Protocol

4.1 STATISTICAL METHODS

This Statistical Analysis Plan provides the details of the statistical analysis of the study data that is described in the protocol.

4.1.1Sample Size

The primary analysis will be the mean change in index joint pain from baseline to 6 months as measured by the Numerical Rating Scale.

The hypothesis to be tested is:

H₀: $\mu_{DMON} = 0$ versus H_A: $\mu_{DMON} > 0$.

In this hypothesis, μ_{DMON} is the mean change in pain on walking from baseline at 6 Months in CINGAL treated patients.

The data will be analyzed via a one sample t-test.

It is assumed that a mean change in pain from baseline of 2 points represents a clinically significant improvement with a standard deviation of 2 - 2.5 points, for 80% power and alpha of 5% then a total of 15 subjects are required. To ensure sufficient subjects are available at the 6 month follow up, it is proposed to enroll and treat at least 25 subjects which should be more than adequate to demonstrate that treatment of the study population with CINGAL would reduce joint pain at 6 months.

Single sites should not enroll more than 75% of the total enrollment.

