This will be analyzed for each of the protocols and tabled like the primary endpoint in section 4.1.2.1.

4.1.3.4 Responder index based on OMERACT- OARSI responder index at 1 Month, 3 Months and 6 Months.

The response rate for each time point will be tabulated and exact 95% confidence intervals will be calculated.

This will be estimated and tested using PROC FREQ with the BINOMIAL option. The results will be displayed similar to:

Summary of the OMERACT-OARSI Responder Rates at each visit and each protocol.

Parameter	1 Week	1 Month	3 Months	6 Months
Estimate n/N (%)				
95% Confidence Interval				

4.1.3.5 Time to Treatment Failure.

The time to treatment failure will be assessed via the estimation of the Kaplan-Meier curve. This will be done via the PROC LIFEREG procedure in SAS. The estimate of the median survival time and the 95% confidence intervals will be reported. This will be done for each protocol.

For all studies, a patient is considered a treatment failure if any of the following occur:

Corticosteroid injections Shock-wave therapy Dry Needling Nitroglycerin patches Prolotherapy (PrT). Platelet / PRP / BMAC injection Hyaluronic Acid. Surgical treatment – open or arthroscopic

4.1.3.6 Reduction in Pain Medication usage at 1 Month, 3 Months and 6 Months.

The reduction from baseline in the mean reduction of medication usage at each time point will be tabulated and 95% confidence intervals will be calculated.

This will be estimated using PROC MEANS. The results will tabled like the primary endpoint in section 4.1.2.1.

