4.1.4 Exploratory Endpoints

Any comparisons across timepoints (baseline to 6 months) not described in the primary or secondary endpoints, including but not limited to:

- Demographics
- Medical History
- History of joint osteoarthritis
- Injection procedure
- Concomitant medications
- Non-drug therapy

For the exploratory analyses, the continuous variables will be summarized via descriptive statistics (n, mean, median, standard deviation, minimum, and maximum. The discrete variables will be summarized via counts and percents.

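### SAP 4.1.3.5 assigns a Kaplan-Meier analysis to PROC LIFEREG, a parametric procedure, and its only numerical summary, the median, may not be reached with 25 subjects over 6 months

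*SAP*

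**What the plan says.** SAP 4.1.3.5 states the method for time to treatment failure as "assessed via the estimation of the Kaplan-Meier curve. This will be done via the PROC LIFEREG procedure in SAS". It then gives the output: "The estimate of the median survival time and the 95% confidence intervals will be reported". The analysis is run separately for each of the three protocols the SAP covers, so the ankle study stands on its own numbers.

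The section lists the events that count as failure. It names no parametric distribution, no failure-free proportion at a fixed time and no fallback if the median is not reached.

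Other relevant places:

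- SAP 2.0 plans up to 25 subjects per study, and "Subject participation will last approximately 6 Months".
- SAP 4.1.1 enrols more than the 15 subjects calculated for the primary endpoint, with the reason "To ensure sufficient subjects are available at the 6 month follow up". Losses are therefore expected, and Protocol 13.12 lists "Subject lost to follow-up" among the withdrawal reasons.
- SAP 4.1.3.4, directly above, plans for the responder endpoint: "The response rate for each time point will be tabulated and exact 95% confidence intervals will be calculated".
- SAP 3.0 also lists treatment failure as exploratory, and SAP 4.1.4 says of exploratory data: "The discrete variables will be summarized via counts and percents".

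**The concern.** There are two separate problems.

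First, the estimator and the procedure do not match. The Kaplan-Meier curve is non-parametric, and in SAS the curve and its median with CI come from PROC LIFETEST. PROC LIFEREG fits parametric models. The mistake need not be visible in the output: a LIFEREG fit would normally still return a median when fewer than half the subjects fail. That figure would be an extrapolation beyond 6 months, governed by a distribution the SAP never names, and a reader could take it for a Kaplan-Meier result.

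Second, even with the right procedure, the one number promised depends on about half the subjects failing. If fewer do, the planned result is a median not reached, and no estimate with a CI is specified in its place.

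**Working it through.** **Inputs.** N = 25 per study (SAP 2.0; SAP 4.1.1). Follow-up is 6 months (SAP 2.0). CI level is 95% (SAP 4.2). The documents give no failure rate and no loss rate, so the 6-month failure probability p and the number lost early c are assumptions. The only sizing figure in the documents, 15 subjects, is for the primary endpoint; there is none for this endpoint to reproduce.

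**Failures needed for a median.** If c subjects are lost before the first failure and the rest are followed to 6 months, n = 25 − c are at risk and S(6) = 1 − d/n after d failures. The median exists once S(6) ≤ 0.5.

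| Lost early (c) | n | Smallest d | S(6) |
|---|---|---|---|
| 0 | 25 | 13 | 12/25 = 0.480 |
| 2 | 23 | 12 | 11/23 = 0.478 |
| 5 | 20 | 10 | 10/20 = 0.500 |
| 10 | 15 | 8 | 7/15 = 0.467 |

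With c = 5 the curve lands exactly on 0.5; if it must fall strictly below, 11 failures are needed. If the losses come after all the failures, 13 are needed whatever c is.

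**Chance that the median exists.** P(X ≥ d), X binomial(n, p):

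| Case | p = 0.2 | 0.3 | 0.4 | 0.5 | 0.6 |
|---|---|---|---|---|---|
| 13 of 25 | 0.0004 | 0.017 | 0.15 | 0.50 | 0.85 |
| 12 of 23 | 0.0006 | 0.021 | 0.16 | 0.50 | 0.84 |
| 10 of 20 | 0.003 | 0.048 | 0.24 | 0.59 | 0.87 |
| 11 of 20 (strict) | 0.0006 | 0.017 | 0.13 | 0.41 | 0.76 |
| 8 of 15 | 0.004 | 0.050 | 0.21 | 0.50 | 0.79 |

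**Failures needed for an upper limit on the median.** The upper 95% limit of S(6) must fall below 0.5. With complete follow-up, Greenwood's formula gives SE = S·√(d/[n(n − d)]).

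- d = 17: S = 0.32, log-log upper limit 0.502. Not enough.
- d = 18: S = 0.28, SE = 0.28 × √(18/(25 × 7)) = 0.090. Linear upper limit 0.28 + 1.96 × 0.090 = 0.456; log-log 0.460; log 0.525.

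So 18 failures are needed with linear or log-log limits, and 19 with log limits. Even at p = 0.5 the chances are P(X ≥ 18) = 0.022 and P(X ≥ 19) = 0.007.

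**What a parametric fit would report.** Take a Weibull with shape k that matches the 6-month failure rate p. Its median is 6 × [ln 2 / (−ln(1 − p))]^(1/k) months.

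| Shape k | p = 0.2 | 0.3 | 0.4 |
|---|---|---|---|
| 0.5 | 57.9 | 22.7 | 11.0 |
| 1 | 18.6 | 11.7 | 8.1 |
| 2 | 10.6 | 8.4 | 7.0 |

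For example, at p = 0.2 and k = 1: 6 × 0.6931/0.2231 = 18.6. Every entry lies beyond the 6 months observed, and the spread comes from the assumed shape.

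**What remains estimable.** The 6-month failure-free proportion does not depend on the median being reached. With log-log limits, 5 failures of 25 give 0.80 (95% CI 0.58 to 0.91); 5 failures with 5 early losses give 15/20 = 0.75 (0.50 to 0.89).

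**The case against.** The firm part of the point is a wrong procedure name. The SAP states the estimator and names no distribution, so a competent programmer asked for a Kaplan-Meier curve would use a procedure that draws one. LIFEREG probability plots can also overlay a non-parametric estimate. The extrapolated medians arise only if the analyst disregards the stated estimator. This is fair as to likelihood. But neighbouring sections name SAS procedures that suit their analyses, so the name reads as an instruction, and nothing elsewhere overrides it. A plot overlay is not the promised median and CI.

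The second part is conditional. No failure rate is given, and at 60% the median would exist with probability 0.85 under complete follow-up. The figures with losses also depend on the loss count and on whether S = 0.5 counts: with 7 or 9 early losses, the chance at a 30% rate is 6.0% or 7.4%. All of that stands. Against a high rate, Protocol 6.6 requires willingness to abstain from other ankle treatments and excludes subjects planning a hyaluronic acid or steroid injection in either joint, and both injections are on the SAP's failure list.

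Finally, a median not reached is a legitimate Kaplan-Meier result, the curve itself shows the failure-free proportion, and counts and percents may appear under SAP 4.1.4. Those concessions are right. What is missing is a CI for that proportion. Counts and percents do not account for censoring, and the list in SAP 4.1.4 does not name treatment failure, although it is open-ended.

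**Conclusion.** The concern holds. As written, SAP 4.1.3.5 does not yield the estimate it promises, because the named procedure is parametric and no distribution is given. With the correct procedure, the only planned number needs 13 of 25 failures under complete follow-up, and fewer if subjects are lost early. At 6-month failure rates of 30% or less, the chance of reaching it is at most about 5% in the cases tabulated above, and an upper confidence limit is unlikely even at 50%. These probabilities rest on assumed failure and loss rates; the mismatch between estimator and procedure does not. The consequence is confined to one descriptive secondary endpoint with no test attached, although the same text governs all three protocols. The primary analysis is unaffected. It should be corrected.

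**What to change.** In SAP 4.1.3.5, replace PROC LIFEREG with PROC LIFETEST. Report the Kaplan-Meier failure-free proportion at 6 months with its 95% CI alongside the median, and show the median or its upper limit as not reached where that applies. State the CI transformation, since it moves the threshold from 18 to 19 failures, and state how subjects without a failure are censored. The cost is a few lines of SAP wording and one extra estimate per protocol. No new data are needed.

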13.4 Protocol Deviations

Deviations from the protocol include, but are not limited to missed assessments, out of window assessments, etc. All protocol deviations will be documented and explained. All subjects with protocol deviations will continue to be followed for improvement and safety. Analysis of study data will be done on both the ITT and PP populations.

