4.1.2 Primary Efficacy Endpoint

4.1.2.1 The mean change in index joint Pain from baseline to 6 Months as measured with NRS comparing the CINGAL treated group to baseline measurements .

The primary analysis will be the mean change in index joint pain from baseline to 6 months as measured by the Numerical Rating Scale.

The hypothesis to be tested is:

H₀: $\mu_{DMON} = 0$ versus H_A: $\mu_{DMON} > 0$.

In this hypothesis, μ_{DMON} is the mean change in pain on walking from baseline at 6 Months in CINGAL treated patients.

The data will be analyzed via a one sample t-test.

This will be analyzed using SAS PROC UNIVARIATE. ODS statements will be used to output the descriptive statistics and p-values into data sets that can be easily displayed using PROC REPORT.

The tables for this analysis will be displayed as follows showing all time points for reference:

This analysis will be performed for each of the protocols

Summary of Differences in Mean Responses over time -

Time Perios			Visit Result	
	Descriptive Statistic	Baseline Result		Change from Baseline
1 Week	N			
	Mean			
	Std.Drv			
	Median			
	(Min,Max)			
	p-value diff=0			
1 Month	N			
	Mean			
	Std.Drv			
	Median			
	(Min,Max)			
	p-value diff=0			
•••				
6 Months	Ν			
	Mean			
	Std.Drv			
	Median			
	(Min,Max)			
	p-value diff=0			

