4.5 SUBJECT POPULATIONS

All safety analyses will be conducted on all subjects who undergo treatment in any group.

The Safety Population will be defined as all subjects who undergo at least one Study Treatment, and the safety analysis will be performed on this population.

The primary analysis on the primary endpoint will be performed on the Intent to Treat (ITT) population, defined as all patients who were treated in the study. All Primary and Secondary endpoints will be analyzed using the ITT population.

A secondary analysis will be conducted on the Per Protocol (PP) population. Since the primary endpoint is at 6 Months, this is all subjects who complete the 6 Month visit and who do not have a major deviation from the protocol. For all other assessments, this is defined as the subjects who complete those assessments according to the protocol.

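### No rule covers a Month 6 score taken after a listed failure therapy in the index ankle, so its relief can count towards Cingal in the primary test and the responder rate

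*SAP*

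**What the plan says.** SAP 4.1.3.5 defines failure by treatment received: "For all studies, a patient is considered a treatment failure if any of the following occur". The list covers corticosteroid, hyaluronic acid, prolotherapy and platelet or marrow injections, shock-wave therapy, dry needling, nitroglycerin patches and surgery. It is not limited to the index joint. The only analysis attached to it is this: "The time to treatment failure will be assessed via the estimation of the Kaplan-Meier curve".

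The primary endpoint in SAP 4.1.2.1 is "The mean change in index joint Pain from baseline to 6 Months as measured with NRS comparing the CINGAL treated group to baseline measurements", analysed by a one-sample t-test. For OMERACT-OARSI, SAP 4.1.3.4 says "The response rate for each time point will be tabulated and exact 95% confidence intervals will be calculated". Neither section mentions failure status.

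Both endpoints use the ITT population, "defined as all patients who were treated in the study" (SAP 4.5). The Per Protocol (PP) population is secondary: "this is all subjects who complete the 6 Month visit and who do not have a major deviation from the protocol". Neither document defines a major deviation.

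Protocol 13.4 keeps deviating subjects under observation: "All subjects with protocol deviations will continue to be followed for improvement and safety". It adds: "Analysis of study data will be done on both the ITT and PP populations". Protocol 13.12 does not name treatment failure among its examples of withdrawal reasons, although those examples are not exhaustive and include an open category.

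**The concern.** A listed therapy in the index ankle is meant to relieve the symptom that the primary endpoint measures. Suppose a subject whose ankle stays painful has a steroid injection at month 4 and attends Month 6. That subject is a failure on the survival curve. The same subject may be an improvement in the primary mean and a responder in the OMERACT-OARSI rate. No control arm shares the later relief, so the comparison with zero attributes it to Cingal.

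PP does not settle the matter. It is unclear whether a failure therapy is a major deviation. If it is, dropping those subjects removes the people in whom Cingal did not work, which also favours the product.

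At stake are the size of the 6-month effect, the responder rate, and the freedom to choose a handling rule after the results are known.

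**Working it through.** **1. The plan's own figure.** Protocol 9.1 and SAP 4.1.1 assume a mean change of 2 points, SD 2 to 2.5, alpha 5% and 80% power, and require 15 subjects. Exact one-sample t-test power (noncentral t) gives n = 15 at SD 2.5, two-sided, with power 82.1%. The figure reproduces. At the 25 subjects planned, power is 97.0% (SD 2.5) to 99.8% (SD 2).

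**2. Inputs for the size of the effect.** N = 25 and SD 2 to 2.5 come from the documents. The number of failures f and the gain d from the other therapy are my assumptions, because the documents give neither. The alternative hypothesis is written one-sided, while the table shell tests for any difference from zero, so both readings are shown.

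**3. Shift in the primary mean.** Shift = f × d / 25.
- f = 1, d = 1: 1/25 = 0.04
- f = 2, d = 1: 2/25 = 0.08
- f = 2, d = 2: 4/25 = 0.16
- f = 5, d = 2: 10/25 = 0.40

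For scale, the observed mean needed for two-sided significance at n = 25 is t(0.975, 24) × SD/5, which is 0.83 at SD 2 and 1.03 at SD 2.5.

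**4. Chance of a positive test if Cingal does nothing.** Simulation of 200,000 trials, n = 25, change drawn from N(0, SD), d added to f subjects, failure unrelated to the underlying change. Ranges run over SD 2.5 to SD 2.

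| f, d | One-sided 5% | Upper tail of two-sided 5% |
|---|---|---|
| none | 5.0% | 2.5% |
| 1, 1 | 5.9–6.0% | 3.0–3.1% |
| 2, 1 | 6.6–7.1% | 3.4–3.7% |
| 2, 2 | 8.6–9.5% | 4.6–5.1% |
| 5, 2 | 17.0–21.1% | 9.8–12.5% |

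**5. Responder rate.** Each failure counted as a responder adds 1/25 = 4 percentage points. As an illustration, 15/25 = 60.0% (exact 95% interval 38.7 to 78.9) becomes 13/25 = 52.0% (31.3 to 72.2) once two failures are non-responders.

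**6. Would setting failures to zero change repair the primary test?** Only if failure is unrelated to the underlying change; the test is then positive in 4.9 to 5.1% of null trials (one-sided). People usually seek another treatment because they hurt, so I let failure track poor change (SD 2, no Cingal effect, one-sided 5%).

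| Scenario | Failures set to 0 | Observed scores |
|---|---|---|
| 2 failures, correlation 0.5 | 10.5% | 8.0% (d = 1), 11.5% (d = 2) |
| Worst 2 of 25 fail | 22.1% | 9.0% (d = 1), 14.4% (d = 2) |
| 5 failures, correlation 0.5 | 19.8% | 28.3% (d = 2) |
| Worst 5 of 25 fail | 57.9% | 38.2% (d = 2) |

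Zero replaces a worsening with no worsening, which can favour Cingal more than the observed score does. Neither rule is better throughout.

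**7. Power for a conservative sensitivity test.** With failures at exactly 0, the others averaging 2 points and a two-sided test, power is 95.6% (SD 2.5) to 99.6% (SD 2) with 2 failures, and about 92% to 99% with 5. The rule proposed under the fix can give values below 0, so these figures are upper limits for it.

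**The case against.** The strongest reply is that observed scores on all treated subjects, with follow-up after deviations, amount to a treatment-policy analysis, which is a recognised choice. Failures are not hidden, because time to failure is reported separately. Subjects must agree to forgo other ankle treatments (Protocol 6.6.1, no. 6), and those planning a steroid or hyaluronic acid injection are excluded (6.6.2, no. 5), so few failures are likely. With 1 or 2, the shift is small against the planned 2 points. A single-arm test against zero already attributes every source of change to treatment, and this is a minor part of that.

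Much of this stands. It supports keeping the observed-score test as primary and ranking the point as a modest improvement. It does not remove the gap. The SAP never states the treatment-policy choice. The entry criteria concern willingness and plans at screening, not how to analyse someone treated later. And time to failure is itself a secondary endpoint, so the sponsor allows for failures.

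A reader might infer that the plan instructs the use of post-failure scores, or that the primary result will be materially inflated. The documents support neither. They are silent, and use of the scores is only the default reading. A failed subject might instead be withdrawn under the open category in Protocol 13.12, which would make this a missing-data question. The OMERACT-OARSI criteria are not set out, so a failure's responder status is unspecified rather than fixed as a response. A material effect needs something like 5 failures in 25, for which the documents give no basis.

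**Conclusion.** The point holds in conditional form. If a subject receives a listed therapy in the index ankle and attends Month 6, no rule keeps the post-therapy score out of the primary t-test or the responder rate, and its relief is then credited to Cingal.

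The effect on the primary mean is small at 1 to 2 failures. The responder rate is the more sensitive of the two endpoints. These sizes rest on assumed failure counts and gains, and there is no bias if no failures occur.

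A reader might also conclude that the primary analysis should be replaced by one with failures set to zero change. That does not follow: such a rule loses control of the 5% level when failure tracks poor response. This is a cheap improvement and not a defect that invalidates the primary test.

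**What to change.** Three changes to the SAP, made before the data are examined:

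1. **SAP 4.1.3.4, add:** 'A subject who meets 4.1.3.5 in the index ankle is a non-responder at every visit after the failure date.'
2. **SAP 4.1.2.1:** keep the observed-score t-test as primary. Pre-specify a sensitivity t-test in which a subject who meets 4.1.3.5 in the index ankle before Month 6 is given the less favourable of 0 and the last change observed before the failure therapy. A subject with no earlier follow-up score gets 0. This gives no credit for later relief and does not erase a worsening already recorded at Month 1 or Month 3. It cannot capture worsening after the last visit before the therapy.
3. **SAP 4.5:** state that 4.1.3.5 failures stay in the PP set under the same rules.

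The words 'in the index ankle' matter, because the current list would also count therapy at another joint.

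The cost is a few SAP sentences and one extra analysis. No new data are needed, since the time-to-failure analysis already requires the failure date and the earlier NRS scores are collected at scheduled visits. The downside is a slightly less favourable responder rate if failures occur.
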